This trial aims to deliver, across a range of UK hospitals, a package of interventions for Acute Kidney Injury (AKI) aimed to improve recognition and quality of care for AKI, and to assess how this translates into better outcomes in AKI patients and if this intervention can reduce the incidence of h-AKI (detailed protocol available on request).

For practical reasons this service can only be applied at the level of the population covered by the hospital and not on a subset of random patients within a hospital. Also the intervention is assumed to have a positive effect on AKI management/outcomes. For these reasons the study has been set up as a stepped-wedge cluster randomised trial (SWCRT), with the intervention applied at a cluster level and applied to all participating units by the end of the study. Such an approach overcomes any ethical problem of withholding a treatment considered likely to be effective, as the entire population recruited will receive the treatment by the end of the study. This approach also allows for differentiation between the effect of the intervention and potential independent unknown time-related factors.

There are no reporting guidelines specific to SWCRTs, so this Statistical Analysis Plan (SAP) is written to be consistent with the extension to cluster randomised trials of the CONSORT 2010 document [Campbell et al., 2012] and further suggestions recently published for SWCRT [Hemming et al, 2015]. This statistical analysis plan will guide the Trial Statistician during the statistical analysis of all quantitative outcomes in order to answer the objectives of the study.

STUDY DESIGN

A Stepped Wedge Cluster Randomised Trial approach will be taken. This means that the intervention will be delivered in sequential steps to one or more units of randomisation per time-period and

delivered to all the units of randomisation by the end of the study. This study has recruited 5 hospitals and is planned to take two years, between December 2014 and November 2016, with 2 initial control periods for all 5 hospitals, followed by 5 steps of randomisation (one hospital per step), and including a transition period (the first 'treatment period', when the treatment is expected not to have reached full efficacy on outcomes), for a total of 8 time-periods, each of 3 months in length (24 months in total – see Table-1, page.6).

THE INTERVENTION

The intervention (protocol, sections 3 and 5, available on request for details), has 3 parts:

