- 4. Length of hospital stay of patients with AKI (patient level data, counts in days, potentially to analyse using Poisson model, depending on the distribution of this outcome)
- 5. Number of critical care bed days used by patients with AKI (patient level data, counts of days in ICU for each patients, possibly to analyse using Poisson or negative binomial model zero inflated, depending on distribution, as many counts of zeros are expected.
- 6. Achievement of complete renal recovery by hospital discharge in AKI patients (with renal recovery defined as serum creatinine returning to a value less than 27 μ mol/l above baseline creatinine value). These are patient level data, binary outcome on all AKI patients (0=did not recover during hospitalisation; 1=recovered during hospitalisation, logistic analysis).

RANDOMISATION UNITS AND TIME-PERIODS

In this trial, the primary outcome will be measured for each episode of AKI detected in patients hospitalised overnight, while the intervention will be implemented at hospital level. Hence this is a cluster randomised trial, where the units of randomisation are the participating hospitals.

In this trial the intervention will be implemented in a total of 5 hospitals, with only one hospital being randomised each time at each step (with a total of 5 randomisation steps), with time periods of 3 months length.

This intervention is complex and would take some time to deliver it. While the electronic detection system has been set up in advance (with results kept suppressed at baseline) and can be activated immediately at start of intervention, teaching to staff will require some time as well as change in practice to be established. For these reasons we expect to observe no quantifiable effects on the outcomes of AKI patients at first after intervention, and hence we have planned to have a transition period. While data on primary and secondary outcomes will be collected for all periods of the study, data from the transition period for each hospital will be excluded from the analyses. As this trial has sufficient power, we have planned for the transition period to be of the same length as the unexposed/exposed time-periods (3 months).

In summary (see Table-1), we are planning to have, for each hospital, two or more control periods (unexposed to the intervention, coded as '0'), one transition period (the first period of intervention,

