The annual number of hospital admissions in the 5 institutions recruited was taken from HSCIC (total annual admissions of about 434,000). We used a conservative assumption of AKI incidence of 2.5% of admissions and 30-days mortality rate after AKI of 16% [Selby 2012], which corresponds to an average of AKI episodes per hospital per 3 months of about N=540. Power was set at 80%, alpha at 0.05 and a range of values for inter class correlation (ICC) between 0.01-0.2 was considered. For the sample size calculations we used a Stata program [Hemming and Girling, 2014], which can accommodate for the transition periods. This showed that with a trial study-time of two years (Dec'14 – Nov'16) using the 5 units, with one unit per randomisation step and with one transition period (as in table-1), we would be able to detect a decrease in mortality from 16% to 12.8%. This corresponds to a reduction of about 20% in 30-days mortality, which is both clinically relevant (equating to around 300 fewer deaths each year for the total of the 5 units) and plausible.

RECRUITMENT AND RANDOMISATION

- Eligibility of hospitals

Considering this trial was starting in parallel to the AKI national program (with the need to temporarily exempt the hospitals recruited) and the knowledge that the numbers of AKI episodes in hospitalised patients are fairly high, we planned to limit the recruitment to only 5 hospitals. For convenience the following 5 units were recruited, 2 from Surrey (Ashford and Frimley Park) and 3 from Yorkshire (Bradford, Leeds General and Leeds St. James).

- Eligibility of patients

Adult patients (≥ 18 yrs) hospitalised overnight in the participating hospitals are eligible if they should present in hospital with AKI or develop an episode of h-AKI, during the study period. In particular, AKI will be identified by having an inpatient blood test that triggers an AKI warning stage result, using the NHS England AKI detection algorithm (<http://www.england.nhs.uk/wp-content/uploads/2014/06/psa-aki-alg.pdf>), both in the control/baseline periods (when results are suppressed, not visible to end-users) and implementation periods.

Patients that are identified as having AKI but were already on chronic dialysis are not eligible and will need to be excluded, while patients with a renal transplant are eligible.

The five hospitals were recruited and the randomisation took place on the 11th of May 2015.

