Randomisation was performed using SAS-9.3 (RANUNI function), to generate 5 random numbers.

These were then allocated to the five hospitals (listed in alphabetical order, based on hospital name), and finally the hospitals were sorted based on their random numbers, from smallest to highest, giving the sequence of randomisation.

DATA SOURCE, COLLECTION AND VALIDATION

Data from hospitals

All data used for the analyses described in this document will be collected as part of routine clinical care, from electronic hospital records. Patient level data will be extracted from the hospitals' PAS for all patients flagged by the AKI electronic detection system. The data extracted will be sent to the UKRR. If data are sent in separate files, each file will need to contain unique patient identifiers to allow subsequent linkage and removal of duplicates by the UKRR.

Data set (see <https://www.thinkkidneys.nhs.uk/wp-content/uploads/2014/12/AKI-Warning-Algorithm-Best-Practice-Guidance-final-publication-0112141.pdf> for details) will include:

- Patient identifiers and demographics:
 - NHS number or Local Patient Identifier
 - Date of birth
 - Gender (M/F/U)
 - Ethnicity (name/code)
- Date of admission and date of discharge
- Primary specialty (text field)
- Charlson co-morbidity score (numeric score) and constituent chronic disease binary scoring (1=present, 0=absent)
- In hospital mortality (numerical field, 1=died in hospital 0=survived to discharge)
- 30 day mortality (numerical field, 1=died within 30days of first AKI warning stage result 0=survived to >30days)
- Date of death (date field)
- Length of hospital stay (numerical, in days)
- ICU admission (1=admitted to ICU during hospital stay, 0=no ICU admission) and ICU admission length of stay (numerical field in days)
- AKI data (see <https://www.thinkkidneys.nhs.uk/wp-content/uploads/2015/01/Transmitting-AKI-Warning-Stage-Data-to-the-UKRR-final.pdf> for detailed specification): initial AKI warning stage (numerical field limited to 1, 2 or 3), highest AKI warning stage (numerical field limited to 1, 2 or 3), time between admission and first AKI Warning stage result (numerical field, in hours), final inpatient creatinine result to assess recovery (numerical field, micromol/l).

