- The analysis of length of hospital stay (see outcome 4, page-5) in patients with AKI will be done with the model most appropriate to the distribution of this outcome. As these data are count data (days in hospital, integers ≥ 1), Poisson analysis with episode-level data, adjusted for clustering at centre, is expected to be appropriate. However if the distribution should be approximate to normal or over-dispersion should be observed, mixed-effect linear regression or negative binomial models will be considered. The same model building sequence will be used as in the logistic analysis of the primary outcome.
- Number of critical care bed days (outcome 5, see page 5), will be analysed based on the distribution of the outcome. This is a count outcome, expected to be zero inflated, therefore a negative binomial analysis will be considered if over-dispersion is observed, or logistic regression if very little dispersion is observed for this outcome (0=No days in ICU, 1=one or more days in ICU).
- For secondary outcome n-6 (recovery of AKI, binary outcome, see page-5), we will use the same analysis as for the primary outcome (mixed-effect logistic regression). In this analysis, if patient should die during hospitalisation before recovery of function, the episode will be counted as a non-recovery, while if patient recovers renal function during hospital stay but then dies, the episode will still be considered as a recovery.

TIMELINE FOR ANALYSIS

	Dec 2014 - Nov 2015				Dec 2015 - Nov 2016				Dec 2016 - Nov 2017			
	D-F	M_M	J-A	S-N	D-F	M_M	J-A	S-N	D-F	M_M	J-A	S-N
Develop statistical analysis plan												
Randomise units to steps												
Baseline period-1												
Baseline period-2												
1st Transition												
2nd Transition												
3rd Transition												
4th Transition												
5th Transition												
Last period, all on treatment												
Provide 1 st report on data												
Statistical analysis and write up												

REFERENCES

Balasubramanian, G., et al., *Early nephrologist involvement in hospital-acquired acute kidney injury: a pilot study*. Am J Kidney Dis, 2011. 57(2): p. 228-34.

Chawla, L.S., et al., *Acute kidney injury and chronic kidney disease as interconnected syndromes*. N Engl J Med, 2014. 371(1): p. 58-66.

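### Recovery (secondary outcome 6) has no rule for episodes with no creatinine after the alert, so a change in re-testing could pass for a change in recovery

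*SAP*

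**What the plan says.** - **Definition and denominator** (SAP, Outcomes Measures, secondary outcome 6). The SAP has "renal recovery defined as serum creatinine returning to a value less than 27" micromol/l above baseline, judged by discharge. It is a "binary outcome on all AKI patients (0=did not recover during hospitalisation; 1=recovered during hospitalisation, logistic analysis"). There is no category for episodes in which recovery was not assessed.
- **Entry to the cohort** (Recruitment and Randomisation, eligibility of patients). "AKI will be identified by having an inpatient blood test that triggers an AKI warning stage result". One such sample is enough; no repeat is required.
- **Data** (Data Source, Collection and Validation, data from hospitals). All data are "collected as part of routine clinical care, from electronic hospital records". The listed item for scoring recovery is the "final inpatient creatinine result to assess recovery". The list shows no sample date or time for it, no count of tests, and no condition that it follow the alert.
- **Special rules** (Analysis of secondary outcomes, outcome 6). "if patient should die during hospitalisation before recovery of function, the episode will be counted as a non-recovery"; a patient who recovers and then dies counts as recovered. Nothing is said about episodes without a later test.
- **Missing data** (Potential Problems). The outcomes expected to be complete are named. Recovery is not among them, and no rule is given for it.
- **Exposure** (The Intervention; Outcomes Measures). Detection results are suppressed in control periods. In exposed periods they are visible, with staff education and a care bundle added.

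**The concern.** The passages leave the final creatinine free to be the alert sample itself. Such an episode is still given a 0 or a 1, although the data say nothing about what happened after the alert.

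If the share of these episodes were the same in control and exposed periods, recovery would be mismeasured, but the comparison would not gain a spurious effect by this route. The difficulty is that re-testing is at clinical discretion and the intervention is "aimed to improve recognition and quality of care for AKI". A visible alert is a plausible reason to repeat a creatinine. The measured outcome would then combine renal recovery with the chance of being re-tested, and the treatment odds ratio would carry both.

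The SAP guards against similar problems elsewhere. It limits the progression outcome to stage 1 and 2 episodes because progression to dialysis cannot be determined for all stage 3 patients. It also plans for laboratory reorganisation that might produce an apparent rise in AKI incidence. Outcome 6 has no comparable protection.

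**Working it through.** **1. Records scored literally** (illustrative values, micromol/l)

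| Record | Baseline | Alert | Later result | Final minus baseline | Code |
|---|---|---|---|---|---|
| Not re-tested | 80 | 130 | none | 130 - 80 = 50 | 0 |
| Re-tested | 80 | 130 | 95 | 95 - 80 = 15 | 1 |

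The two patients may have the same kidney function at discharge. The opposite error is also possible: an alert value less than 27 above baseline would be coded 1 with no repeat test. The SAP does not give the alert thresholds, so how often this happens cannot be said.

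**2. Measured recovery**

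Let u be the share of episodes with no post-alert creatinine, r the recovery proportion among the re-tested, and q the share of untested episodes whose alert value is less than 27 above baseline.

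Measured recovery = (1 - u) × r + u × q

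With r and q the same in both conditions, exposed minus control = (u_control - u_exposed) × (r - q). A fall in u therefore moves the result towards benefit when q is below r. The shift is largest at q = 0, which is used below.

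**3. Illustration with no true effect**

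The SAP gives neither u nor r. Assumed: r = 50% to 70%, q = 0, in-hospital deaths ignored.

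| Untested, control to exposed | r | Measured recovery, control to exposed | Odds ratio |
|---|---|---|---|
| 10% to 7% | 50% | 45.0% to 46.5% | (0.465/0.535)/(0.450/0.550) = 1.06 |
| 10% to 7% | 70% | 63.0% to 65.1% | (0.651/0.349)/(0.630/0.370) = 1.10 |
| 15% to 10% | 50% | 42.5% to 45.0% | (0.450/0.550)/(0.425/0.575) = 1.11 |
| 15% to 10% | 70% | 59.5% to 63.0% | (0.630/0.370)/(0.595/0.405) = 1.16 |
| 20% to 10% | 50% | 40.0% to 45.0% | (0.450/0.550)/(0.400/0.600) = 1.23 |
| 20% to 10% | 70% | 56.0% to 63.0% | (0.630/0.370)/(0.560/0.440) = 1.34 |

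With no change in u, the odds ratio is 1.00.

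**4. Could the trial detect a shift of this size?**

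The SAP states no figure for recovery, but its cell size reproduces: 434,000 × 0.025 / 5 / 4 = 542.5, against about 540 stated. I used the Hussey and Hughes variance with 5 hospitals, 8 periods, transition cells dropped, each hospital in control until its step, 540 episodes per cell, ICC 0.01 (the low end of the SAP's range) and two-sided alpha 0.05. The standard error of the risk difference is 0.01208 at a proportion of 16%, and it scales with the square root of p(1 - p).

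For untested falling from 20% to 10% at r = 50%, the mean proportion is 0.425:

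- standard error = 0.01208 × √(0.425 × 0.575 / (0.16 × 0.84)) = 0.0163
- 0.05 / 0.0163 = 3.07, and 3.07 - 1.96 = 1.11, so the chance of a significant result is about 87%

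Over r = 50% to 70% the chance is 87% to 99%. For a fall from 20% to 15% (odds ratio 1.11 to 1.15) it is 34% to 58%. With equal re-testing it is the nominal 5%.

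**5. What the added analyses would show**

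Take untested falling from 15% to 10% and code every untested episode as recovered:

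- r = 70%: control 0.595 + 0.15 = 0.745, exposed 0.630 + 0.10 = 0.730; odds ratio (0.730/0.270)/(0.745/0.255) = 0.93
- r = 50%: control 0.425 + 0.15 = 0.575, exposed 0.450 + 0.10 = 0.550; odds ratio (0.550/0.450)/(0.575/0.425) = 0.90

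Set beside 1.16 and 1.11 with all coded not recovered, the two codings fall on either side of 1. A reader would then see that the finding depends on the untested episodes.

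**The case against.** The other side has five fair arguments.

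- **The coding is implied, not stated.** A reader might infer that the SAP orders untested patients to be coded as not recovered. It does not. The coding follows from combining the all-episode denominator, the single final value, entry on one sample and the lack of any other rule. The reference to creatinine returning to a value could be read as requiring a later measurement, and alert values under the margin would be coded the other way. This stands. It also shows that the rule is left open.
- **The field list may be abbreviated.** It omits baseline creatinine, which outcome 6 needs, and points to a linked specification not available here. The text on laboratory reorganisation says the AKI dataset holds the creatinine values used in the alert. Some screening may therefore already be possible, although equal values do not prove that two results are the same sample.
- **Differential re-testing is assumed.** A reader might infer that the recovery result will be biased towards benefit. The SAP does not support that. It leaves the details of the intervention to the protocol, gives no re-test rates, and describes the detection results as suppressed, not the creatinine results themselves.
- **Restricting the analysis to re-tested episodes is no clean remedy.** It conditions on care given after exposure. If visible alerts extend testing to milder cases, the exposed re-tested group is healthier and the odds ratio still moves. Keeping all episodes is a defensible main analysis.
- **Only a secondary outcome is involved.** That is so, and it limits the weight of the point.

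None of this supplies a rule for the untested episodes or lets a reader see how many there are.

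**Conclusion.** The point holds as a gap in the definition of outcome 6. As written, episodes with no creatinine after the alert are classified by the alert value, in either direction, and nothing planned would show how many there are or whether their share changes with exposure. A favourable recovery result could not then be told apart from more frequent blood testing.

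The size is conditional. The odds ratios of 1.06 to 1.34 rest on assumed re-test and recovery rates, on no true effect, and on untested alert values lying at or above the margin. They show that modest changes in re-testing would matter; they do not estimate the bias in this trial. The significance probabilities depend in addition on the cell size, ICC and step pattern used. The change should be made because it is cheap and decides how outcome 6 can be read. The primary outcome does not depend on it.

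**What to change.** - Keep all AKI episodes in the main analysis of outcome 6, and state in the SAP how an episode with no post-alert creatinine is coded there.
- Identify these episodes from the date and time of the final creatinine, or from a flag that the final sample is the alert sample. The alert creatinine values already described in the dataset can serve as a preliminary screen.
- Report the share of such episodes by hospital and by control or exposed status.
- Add two sensitivity analyses with the same model: these episodes all coded not recovered, and all coded recovered. Deaths before recovery stay coded as non-recovery in both. Because each applies one coding to both conditions, they are not worst-case limits and should not be described as such.
- If wanted, show an analysis limited to re-tested episodes as a further sensitivity analysis, noting that it conditions on care after exposure and can bring its own selection bias.

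The cost is one field or flag from the laboratory record, a short paragraph in the SAP, one descriptive table and a few extra model fits. No episodes are lost from the main analysis.

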- An AKI electronic detection system within pathology laboratory software
- An educational program to raise awareness and knowledge of AKI in care workers at hospital
- An AKI care bundle

The AKI electronic detection system has already been mandated at a national level (England only), with the plan to start nationwide from April 2015. The 5 hospital recruited for this SWCRT have been exempted from the initiative for the time being, so they would be able to wait to implement the intervention at their assigned time of randomisation, while having the electronic detection system in place since the end of 2014, but silent (as to measure the incidence of AKI during the baseline periods, with no active intervention).

OUTCOMES MEASURES

The outcomes of this study will be measured for all adult patients hospitalised overnight in the 5 participating hospitals, and identified as having an episode of AKI while in hospital by the pathology laboratory detection system (with results suppressed, non-visible to end-users, during control periods). The outcomes will be measured for the entire length of the study-period (1st Dec 2014 to 30th Nov 2016) for all of the AKI events, so multiple entries per patient are possible.

Primary outcome

- Thirty-day mortality after an episode of AKI. These are patient level data, binary outcome (0=patient alive 30 days after the AKI episode; 1=patient dead 30days after the AKI episode, logistic analysis).

Secondary outcomes

- 1. Incidence of h-AKI (aggregate data, counts, number of h-AKI cases, defined as AKI developed after >24hrs in hospital, with the denominator at risk being the total overnight hospitalisation episodes, Poisson analysis, standardised).

- 2. Incidence of AKI progression (defined as AKI that increases by at least one stage of AKI from AKI-stage at time of first detection) during hospitalisation. These are patient level data, binary outcome for each episode of AKI (0=did not progress during hospitalisation; 1=progressed during hospitalisation, logistic analysis).
As we will not be able to determine for all patients diagnosed with level-3 AKI if they progress to need of acute dialysis during hospitalisation, we will perform this analysis to the cohort of AKI level-1 and level-2 episodes only.
- 3. Incidence of individual AKI stages (stage 1, stage 2 and stage 3). These are aggregate data, counts, to analyse as secondary outcome n-1.

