- Data on population at risk: For each of the 3-months periods, the total number of hospital admissions in adult patients (≥ 18 yrs old, elective and non-elective admissions, excluding day case contacts and patient discharged directly from ED) will be needed to estimate the population at risk to analyse incidence of AKI. If possible, hospitals will return a file containing the full list of those admissions, without any patients' identifier, but containing age (rounded to unit), gender and ethnicity of patients. This will allow the statistician to perform a standardised analysis of AKI incidence rates, without having to pre-specify to the hospitals the level of standardisation. If this is not possible, the total number of admission should be given,

preferentially by age-group (18-<25, 25-<30, 30-<35 and so on in 5-years age-bands), gender and ethnicity (South Asian, Black, Other (including mixed race and Chinese), White and Missing).

While the hospitals are responsible for identifying and excluding patients that were in day-care or were already receiving chronic dialysis, the data item 'time between admission and first AKI Warning stage result' will allow the analysts at the UKRR to distinguish episodes of community-acquired AKI and hospital-acquired AKI. Any hospital that should not be able to automatically apply the exclusion of those patients already on dialysis will need to provide the UKRR with necessary extra variables to identify these patients.

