The as-treated analysis will include all cases of AKI as ‘control’ or ‘treated’ based on the treatment that patients had received at time of AKI episode, rather than the treatment they were assigned based on the allocation process. In this case 1st day of the month when e-alert was activated in each hospital will be considered the start of that hospital’s transition period.

The report will include adherence to the timing of randomisation to intervention.

NOTE: If a logistic model should not run/iterate then we will use an equivalent mixed-effects linear regression analysis, approximating by using 0 and 1 as a continuous variable for the dichotomous variable of 30 days mortality (Hussey and Hughes, 2007).

Analysis of secondary outcomes

- The aggregate-data secondary outcomes 1 and 3 (incidence of h-AKI and incidence of AKI by level of AKI - expressed as number of patients developing AKI per hospitalised population), will be analysed using a Poisson regression, standardised by age and gender and, if possible, by ethnicity.

This will be a cluster-level Poisson analysis, with one measure per time-period per hospital, if unadjusted (or one measure per time-period per hospital per age-gender subgroup, if standardised).

MODEL
$$\text{Log}(Y_{ij}) = \log(\text{exposure}_{ij}) + \theta * T_{ij} + \gamma_j + \alpha_i$$

Where Y_{ij} = count of AKI episodes in hospital I at time J

Exposure-ij=denominator, number of hospitalisations in hospital I at time J

θ = effect of the treatment variable (T=1 exposed, T=0 control) in centre I at time J

γ = effect of Time (vector if effect not linear)

(+ ωQ_{ij} in the model if we want to investigate interaction between Time and Treatment)

- For secondary outcome n-2 (progression of AKI, binary outcome), we will use the same analysis as for the primary outcome (mixed-effect logistic regression), limited to the cohort of episodes classified as level-1 and level-2 AKI at time of first detection.

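### The admissions count requested from hospitals has no overnight condition, so it does not match the overnight denominator that the SAP sets for secondary outcomes 1 and 3.

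*SAP*

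**What the plan says.** Under Outcomes measures, secondary outcome 1 (incidence of h-AKI) is defined "with the denominator at risk being the total overnight hospitalisation episodes". Secondary outcome 3 (incidence of individual AKI stages) is to be analysed in the same way. The case population is overnight too. The same section opens with "The outcomes of this study will be measured for all adult patients hospitalised overnight in the 5 participating hospitals", and Eligibility of patients says that adults "hospitalised overnight in the participating hospitals are eligible if they should present in hospital with AKI or develop an episode of h-AKI". Under Number of participants, the text and Table-2 present overnight hospitalisations by hospital and time-period.

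The request to hospitals is in Data source, collection and validation, under the item on the population at risk. It covers adult "elective and non-elective admissions, excluding day case contacts and patient discharged directly from ED) will be needed to estimate the population at risk". If possible, hospitals send a list of these admissions "without any patients' identifier, but containing age (rounded to unit), gender and ethnicity of patients". Otherwise they send totals, preferably split by age-group, gender and ethnicity.

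In Analysis of secondary outcomes, the Poisson exposure is the "denominator, number of hospitalisations in hospital I at time J", with no statement of whether these are overnight.

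**The concern.** The request removes day cases and direct discharges from ED, but it does not require an overnight stay. A non-elective patient admitted to a ward or assessment unit and sent home the same day falls under neither exclusion. That patient enters the denominator but not the numerator, because cases must have stayed overnight. For outcome 1 this holds by definition as well, since h-AKI is "defined as AKI developed after >24hrs in hospital".

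The analyst cannot repair this afterwards. The AKI case file carries admission and discharge dates and length of stay, so the numerator can be restricted to overnight stays. The denominator file lists none of these. As written, the request also cannot supply the overnight counts that Table-2 is meant to show.

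Reducing h-AKI is one of the trial's stated aims. The SAP already plans for one artefact in incidence, the re-organisation of laboratories, which could raise the number of AKI episodes detected. It has no matching safeguard for a change in the make-up of the denominator.

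**Working it through.** **The plan's own figure.** The one stated number that rests on an admissions denominator is the average AKI count in Sample size calculation: 434,000 × 0.025 / 5 hospitals / 4 quarters = 542.5, against about 540 stated. It reproduces. It does not give the same-day share of admissions, so the shares below are assumptions.

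**Effect on absolute incidence.** Let s be the same-day share of the requested admissions. Requested admissions = overnight stays / (1 − s), so reported incidence = overnight incidence × (1 − s). With s = 10%, 20% or 30%, reported incidence is 0.90, 0.80 or 0.70 of the value that the outcome definition calls for.

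**Effect within one hospital, before any modelling.** With cases and overnight stays unchanged, the apparent ratio of exposed to control periods is (1 − s_exposed) / (1 − s_control):

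- 20% to 20%: 0.80/0.80 = 1.00
- 20% to 22%: 0.78/0.80 = 0.975
- 20% to 25%: 0.75/0.80 = 0.9375
- 20% to 30%: 0.70/0.80 = 0.875
- 20% to 15%: 0.85/0.80 = 1.0625

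**Effect on the estimate from the planned model.** The SAP's model compares hospitals within periods as well as periods within hospitals, so the ratios above are not in general what it returns. A Poisson model with log offset, treatment, hospital effects and period effects was fitted to data with no true effect. The layout had five hospitals and eight periods. Each hospital's transition period was dropped and all earlier periods were taken as control, as the text under Randomisation units and time-periods describes. Hospital effects were fixed, standing in for the SAP's cluster term. Same-day shares start at 20% unless stated.

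| Assumed same-day share | Estimated rate ratio (true value 1.00) |
|---|---|
| Constant within each hospital, differing between hospitals | 1.000 |
| Same trend in all hospitals from the same base | 1.000 |
| Same added trend on differing hospital bases | 1.002 |
| One hospital, 20% to 25% at its own step | 0.983 to 0.991 |
| One hospital, 20% to 30% at its own step | 0.966 to 0.982 |
| One hospital, 20% to 30% from period 5 | 0.97 to 1.05 |
| All five, 20% to 25%, each in step with exposure | 0.9375 |
| All five, 20% to 30%, each in step with exposure | 0.875 |
| All five, 20% to 15%, each in step with exposure | 1.0625 |

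The ranges in the one-hospital rows come from which place in the sequence that hospital holds. In the period-5 row, the ratio is lowest when the second hospital in the sequence changes and highest when the last one does.

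**The case against.** The strongest reply is that the intended denominator is already clear. The outcome definition and Table-2 both say overnight, so the request can be read as a working description of the same quantity for hospital data teams, with the model's unqualified term as shorthand. That may well be the intent. But the listed exclusions do not remove same-day non-elective admissions, hospitals extract from the wording of the request, and five sites could interpret it differently. The reply shows that the remedy is small, not that the texts agree.

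Two stronger readings are tempting and should not be drawn.

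- **A false fall of 6% or 12.5%.** A reader might infer that a rise in one hospital's same-day share from 20% to 25% or 30% would appear in full as an intervention effect. It would not. Those figures (0.94 and 0.875) are the raw within-hospital ratios, and the model returns them only if all five hospitals shift by that amount, each in step with its own crossover. Nothing in the SAP suggests this: the step order is randomised, and no route is described by which alerts, education and a care bundle would change same-day admissions. A false rise is also possible.
- **A denominator of stays longer than 24 hours for outcome 1.** Because h-AKI needs more than 24 hours in hospital, a reader might infer that shorter overnight stays should also be removed. The outcome definition explicitly chooses overnight episodes. Replacing that with longer stays would change the quantity estimated, not reconcile two passages.

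The limit on scope also stands. Thirty-day mortality, its sample size and the other patient-level outcomes do not use this denominator.

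**Conclusion.** The concern holds as a contradiction within the SAP: followed as written, the request yields a denominator other than the one that the outcome definition and Table-2 specify, and the file cannot be corrected later. Absolute incidence for outcomes 1 and 3 is understated by the same-day share, whatever that is.

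For the intervention effect, the consequence is conditional and probably modest. It is nil under a stable share or a proportional change common to all hospitals. It is about 1% to 3% for the assumed one-hospital changes at that hospital's own step, and between 0.97 and 1.05 for a one-hospital change from 20% to 30% at period 5. Larger distortions need a coordinated shift that the document gives no reason to expect. All of these sizes rest on assumed shares and on the simplified model described above. The point deserves correction because the mismatch is plain, cannot be checked afterwards and is cheap to remove.

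**What to change.** Reword the population-at-risk request to adult admissions with at least one overnight stay, meaning a discharge date after the admission date. Add length of stay to the anonymised admissions file so that the UKRR can check the filter. Hospitals that can send only totals should apply the filter themselves and confirm that they did.

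Then use the same overnight denominator in all four places: the outcome definition, the data request, the participants table and the exposure term of the Poisson model. Keep the overnight definition for outcome 1.

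The cost is one filter and one extra column in an extract already planned for every quarter, plus consistent wording in the SAP. If any quarters have already been extracted under the present wording, those counts would need to be re-run with the filter.
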